4.4 END OF STUDY DEFINITION

The end of the study is defined as the date of the last visit of the last participant in the study or last scheduled procedure shown in the Schedule of Activities for the last participant in the trial globally.

5 STUDY POPULATION

Prospective approval of protocol deviations to recruitment and enrollment criteria, also known as protocol waivers or exemptions, is not permitted.

5.1 INCLUSION CRITERIA

The inclusion criteria listed in the master protocol are only those applicable to all the participants common to all substudies. For additional substudy specific criteria, refer to the particular substudy.

Participants are eligible to be included in the study only if all of the following criteria apply:

Age

I 01. Participant must be ≥ 18 years of age (or country's legal age of majority if >18 years), at the time of signing the informed consent.

Type of participant and disease characteristics

I 02. Measurable disease:

At least 1 measurable lesion per RECIST 1.1 criteria. Target lesions may be located in a previously irradiated field if there is documented radiographic disease progression in that site.

Weight (not applicable)

Sex, contraceptive/barrier method and pregnancy testing requirements

I 03. All (male and female)

Contraceptive use by men and women should be consistent with local regulations regarding the methods of contraception for those participating in clinical studies.

A) Male participants

Male participants are eligible to participate if they agree to the following during the intervention period and for at least 3 days [corresponding to time needed to eliminate SAR444245] after the last dose of SAR444245:

- Refrain from donating or cryopreserving sperm
PLUS either:
 - Be abstinent from heterosexual intercourse as their preferred and usual lifestyle (abstinent on a long term and persistent basis) and agree to remain abstinent

OR

- Must agree to use contraception/barrier as detailed below

A male condom with female partner use of an additional highly effective contraceptive method with a failure rate of <1% per year as described in [Section 10.4](#) Appendix 4 when having sexual intercourse with a woman of childbearing potential (WOCBP) who is not currently pregnant, or during homosexual intercourse.

B) Female participants

A female participant is eligible to participate if she is not pregnant or breastfeeding, and at least one of the following conditions applies:

- Is not a WOCBP

OR

- Is a WOCBP and agrees to use a contraceptive method that is highly effective (with a failure rate of <1% per year), with low user dependency, as described in [Section 10.4](#) Appendix 4 during the intervention period (to be effective before starting the intervention) and for at least 120 days (for Cohort A, B1, B2, B3, C, and D1) or 60 days (for Cohort D2) [corresponding to the time needed to eliminate any study intervention(s)-] after the last dose of study intervention and agrees not to donate or cryopreserve eggs (ova, oocytes) for the purpose of reproduction during this period.
- A WOCBP must have a negative highly sensitive pregnancy test (as required by local regulations) within 72 hours before the first dose of study intervention.
- Additional requirements for pregnancy testing during and after study intervention are located in Appendix 4

The Investigator is responsible for review of medical history, menstrual history, and recent sexual activity to decrease the risk for inclusion of a woman with an early undetected pregnancy

Informed Consent

I 04. Capable of giving signed informed consent as described in [Section 10.1](#) Appendix 1 which includes compliance with the requirements and restrictions listed in the informed consent form (ICF) and in this protocol.

5.2 EXCLUSION CRITERIA

Participants are excluded from the study if any of the following criteria apply. For additional individual substudy specific criteria, refer to the particular substudy:

Medical conditions

E 01. Eastern Cooperative Oncology Group (ECOG) performance status of ≥ 2 .
E 02. Predicted life expectancy ≤ 3 months.

E 03. Active brain metastases or leptomeningeal metastases.

- Patients with previously treated brain metastases are eligible provided they are clinically stable for **at least 4 weeks** with no evidence of new or enlarging brain metastases and have not received corticosteroids at least 2 weeks prior to first IMP administration.
- Patients with asymptomatic brain metastases (ie, no neurological symptoms, no requirements for corticosteroids, and no lesion >1.5 cm) are eligible but will require regular imaging of the brain as a site of disease as per protocol tumor assessment (TA) schedule.

E 04. History of allogenic tissue/solid organ transplant.

E 05. Treatment-related immune-mediated (or immune-related) AEs from immune-modulatory agents (including but not limited to anti-PD-1/PD-L1 agents and anti-cytotoxic T lymphocyte associated protein 4 monoclonal antibodies) that caused permanent discontinuation of the agent, or that were Grade 4 in severity.

E 06. Last administration of prior antitumor therapy (chemotherapy, targeted agents, and immunotherapy) or any investigational treatment within 28 days or less than 5 times the half-life, whichever is shorter; major surgery within 28 days prior to first IMP administration.

E 07. Comorbidity requiring corticosteroid therapy (>10 mg prednisone/day or equivalent) within 2 weeks of IMP initiation. Inhaled or topical steroids are permitted, provided that they are not for treatment of an autoimmune disorder. Participants who require a brief course of steroids (eg, as prophylaxis for imaging studies due to hypersensitivity to contrast agents) are not excluded.

E 08. Antibiotic use (excluding topical antibiotics) ≤ 14 days prior to first dose of IMP, or any serious systemic fungal, bacterial, viral (excluding viral infection settings as described in [E 15](#)), or other infection that is not controlled.

E 09. Severe or unstable cardiac condition within 6 months prior to starting study treatment, such as congestive heart failure (New York Heart Association Class III or IV), cardiac bypass surgery or coronary artery stent placement, angioplasty, left ventricular ejection fraction (LVEF) below 50%, unstable angina, medically uncontrolled hypertension (eg, ≥ 160 mmHg systolic or ≥ 100 mmHg diastolic), uncontrolled cardiac arrhythmia requiring medication (\geq Grade 2, according to NCI-CTCAE v5.0), or myocardial infarction.

E 10. Ongoing AEs (caused by any prior anti-cancer therapy \geq Grade 2 (NCI-CTCAE Version 5.0). Participants with Grade 2 peripheral neuropathy, or Grade 2 alopecia, are permitted. Participants with endocrine-related AEs Grade ≤ 2 requiring treatment or hormone replacement may be eligible.

E 11. Active, known, or suspected autoimmune disease that has required systemic treatment in the past 2 years (ie, with use of disease modifying agents, corticosteroids or immunosuppressive drugs), except controlled by replacement therapy (eg, thyroxine, insulin, or physiologic corticosteroid replacement therapy for adrenal or pituitary insufficiency, etc). The following are not exclusionary: vitiligo, childhood asthma that has resolved, psoriasis that does not require systemic treatment.

E 12. History of (non-infectious) pneumonitis / interstitial lung disease that required steroids or has current pneumonitis / interstitial lung disease.

E 13. Participant who has received prior radiotherapy within 2 weeks of start of study intervention. Participants must have recovered from all radiation-related toxicities, not require corticosteroids, and not have had radiation pneumonitis. A 1-week washout is permitted for palliative radiation (\leq 2 weeks of radiotherapy) to non-CNS disease.

E 14. Receipt of a live or live attenuated-virus vaccine within 28 days of planned treatment start. Seasonal flu vaccines that do not contain live virus are permitted.

E 15. HIV-infected participants with a history of Kaposi sarcoma and/or Multicentric Castleman Disease or known uncontrolled infection with HIV. HIV-infected participants must be on anti-retroviral therapy (ART) and have a well-controlled HIV infection/disease defined as:

- Participants on ART must have a CD4+ T-cell count >350 cells/mm³ at time of screening.
- Participants on ART must have achieved and maintained virologic suppression defined as confirmed HIV RNA level below 50 copies/mL or the lower limit of qualification (below the limit of detection) using the locally available assay at the time of screening and for at least 12 weeks prior to screening.
- Participants on ART must have been on a stable regimen, without changes in drugs or dose modification, for at least 4 weeks prior to study entry (Day 1).
- Combination ART regimen must not contain any antiretroviral medications other than: abacavir, dolutegravir, emtricitabine, lamivudine, raltegravir, rilpivirine, or tenofovir. See instructions specific to Germany and Italy at screening in Appendix 2 ([Section 10.2](#)) and Appendix 7 (see [Section 10.7](#)).

E 16. Known uncontrolled hepatitis B infection, known untreated current hepatitis C infection, active tuberculosis, or severe infection requiring parenteral antibiotic treatment.

- To control HBV infection, participants with positive HBsAg should have started anti-HBV therapy before initiation of IMP. Antiviral therapy for HBV must be given for at least 4 weeks and HBV viral load must be less than 100 IU/mL prior to first dose of study drug. Participants on active HBV therapy with viral loads under 100 IU/mL should stay on the same therapy throughout study treatment.

- Participants who are positive for anti-hepatitis B core antibody HBc, negative for hepatitis B surface antigen (HBsAg), and negative or positive for anti-hepatitis B surface antibody (HBs), and who have an HBV viral load under 100 IU/mL, do not require HBV anti-viral prophylaxis.
- Participants with past or ongoing HCV infection will be eligible for the study. The treated participants must have completed their treatment at least 1 month prior to starting study intervention. Participants with positive HCV antibody and undetectable HCV RNA without anti-HCV therapy are eligible.

See instructions specific to Germany and Italy at screening in Appendix 2 ([Section 10.2](#)) and Appendix 7 (see [Section 10.7](#)).

E 17. Known second malignancy either progressing or requiring active treatment within the last 3 years. Participants with non-melanomatous skin cancer or cervical cancer that has been curatively surgically resected are eligible.

E 18. Known severe hypersensitivity (\geq Grade 3) to or contraindication for the use of any study intervention or components thereof, including premedication to be administered in this study, as well as PEG or any pegylated drug and *E. coli*-derived protein.

E 19. Participants with baseline SpO₂ \leq 92% (without oxygen therapy).

Prior/concomitant therapy

E 20. Has received prior IL2-based anticancer treatment.

E 21. Is unable or unwilling to take premedication.

E 22. Participants treated under anti-hypertensive treatment who cannot temporarily (at least 36 hours) withhold antihypertensive medications prior to each IMP dosing.

Prior/concurrent clinical study experience

E 23. Current enrollment or past participation in a study of an investigational treatment or an investigational device within 28 days prior to the first dose of study treatment.

Note: Participants who have entered the follow-up phase of an investigational study may participate as long as it has been 28 days after the last dose of the previous investigational treatment.

Organ and bone marrow function

E 24. Absolute neutrophil count <1500 /uL (1.5×10^9 /L) (after at least one week off G-CSF).

E 25. Platelets $<75 \times 10^3$ u/L for participants in Cohort C and platelets $<100 \times 10^3$ u/L for participants in all other cohorts (after at least 3 days without platelet transfusion).

- E 26. Hemoglobin <9 g/dL (without packed red blood cell [pRBC] transfusion within prior 2 weeks). Participants can be on stable dose of erythropoietin (\geq approximately 3 months).
- E 27. Total bilirubin $>1.5 \times$ upper limit of normal (ULN) unless direct bilirubin \leq ULN (Participants with known Gilbert disease who have serum bilirubin level $\leq 3 \times$ ULN may be enrolled).
- E 28. Aspartate aminotransferase and/or alanine aminotransferase $>2.5 \times$ ULN (or $>5 \times$ ULN for participants with liver metastases or participants in Cohort C).
- E 29. Estimated glomerular filtration rate (eGFR) <50 mL/min/1.73 m² (Modification of Diet in Renal Disease [MDRD] Formula).
- E 30. International Normalized Ratio (INR) or Prothrombin Time (PT) (or Activated Partial Thromboplastin Time [aPTT]) $>1.5 \times$ ULN unless the participant is receiving anticoagulant therapy as long as PT or aPTT is within therapeutic range of intended use of anticoagulants.

Other exclusions

- E 31. Individuals accommodated in an institution because of regulatory or legal order; prisoners or participants who are legally institutionalized.
- E 32. Any country-related specific regulation that would prevent the participant from entering the study - see [Section 10.7](#) Appendix 7 (country-specific requirements).
- E 33. Participant not suitable for participation, whatever the reason, as judged by the Investigator, including medical or clinical conditions, or participants potentially at risk of noncompliance to study procedures.
- E 34. Participants are employees of the clinical study site or other individuals directly involved in the conduct of the study, or immediate family members of such individuals (in conjunction with section 1.61 of the ICH-GCP Ordinance E6).
- E 35. Any specific situation during study implementation/course that may raise ethics considerations.
- E 36. History or current evidence of any condition, therapy that might confound the results of the trial, interfere with the subject's participation for the full duration of the trial, or is not in the best interest of the subject to participate, in the opinion of the treating Investigator.

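### E 16 gives opposite answers for participants with known, untreated hepatitis C and detectable RNA

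*Protocol*

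**What the plan says.** Section 5.2 of the master protocol introduces its list with "Participants are excluded from the study if any of the following criteria apply". E 16 then names the infections that exclude: "Known uncontrolled hepatitis B infection, known untreated current hepatitis C infection, active tuberculosis, or severe infection requiring parenteral antibiotic treatment".

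The HCV bullet under E 16 has three sentences:

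1. "Participants with past or ongoing HCV infection will be eligible for the study".
2. "The treated participants must have completed their treatment at least 1 month prior to starting study intervention".
3. "Participants with positive HCV antibody and undetectable HCV RNA without anti-HCV therapy are eligible".

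The Germany entry in Section 10.7 (Appendix 7) reprints the lead sentence and the bullet in the same words, and adds that hepatitis B and C serology is tested at screening. For Cohort A, Section 5.2 of substudy 01 only points back to the master protocol.

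**The concern.** The lead sentence turns away a participant whose HCV is current, known and untreated. The first sentence of the bullet admits anyone whose infection is *ongoing*, without qualification. A person with untreated, viraemic HCV fits both descriptions, so the same criterion both excludes and admits that person.

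What is at stake is consistent enrollment. One site could apply the lead sentence and refuse; another could apply the bullet and enroll, and each could point to protocol text. Section 5 rules out waivers, so the criterion has to be readable as written. Hepatotoxicity is a listed risk for SAR444245 (master protocol, Table 5) and for pembrolizumab (substudy 01, Table 11), so viral hepatitis is a sensible place to want one clear rule.

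**Working it through.** No arithmetic applies. The check sets each HCV status against the two parts of E 16.

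| HCV status | Lead sentence | HCV bullet | Result |
|---|---|---|---|
| Treated, therapy finished at least 1 month before the first dose | Does not reach it | Eligible (sentences 1 and 2) | Eligible, no conflict |
| Still on therapy, or finished less than 1 month before | Does not reach it | Fails sentence 2 | Not eligible, no conflict |
| Antibody positive, untreated, RNA undetectable | Can be read as not current infection | Eligible (sentence 3) | Eligible, no real conflict |
| Known, untreated, RNA detectable | Excluded | Eligible (sentence 1); sentences 2 and 3 do not reach it | **Conflict** |

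The conflict is confined to the last row. The next step was to look for text elsewhere that settles it.

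- **Opening rule of Section 5.2.** Any one criterion suffices to exclude. This favours exclusion if the lead sentence stands alone, but it does not say whether the bullet is an exception to that sentence.
- **E 03.** Bullets in this list can work as exceptions to their heading. E 03 excludes active brain metastases, then says "Patients with asymptomatic brain metastases (ie, no neurological symptoms, no requirements for corticosteroids, and no lesion >1.5 cm) are eligible". A site could read the HCV bullet the same way.
- **E 08.** It excludes "or any serious systemic fungal, bacterial, viral (excluding viral infection settings as described in" E 15) infection that is not controlled. The carve-out covers E 15 (HIV) and not HCV. That leans towards exclusion, but only for infection judged serious and uncontrolled.
- **Appendix 2, Table 4, footnote f.** HCV RNA must be determined after positive serology. No eligibility limit is attached to the result.
- **Section 10.7, Germany.** It repeats the conflict. The Italian entry adds serology only.
- **Substudy 01, Section 5.2.** It refers back to the master protocol, so nothing settles the point for Cohort A.

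Section 5.2 of substudy 02 and all of substudy 03 (Cohort C, hepatocellular carcinoma) are outside the text at hand. The finding is therefore verified for the master protocol and Cohort A only.

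**The case against.** The strongest reply is that E 16 can be read coherently. The lead sentence is the specific rule and sentence 1 of the bullet the general one. Sentence 3 admits untreated participants only when RNA is undetectable, and it would be pointless if every untreated infection were already eligible. *Ongoing* could mean infection that persists after completed therapy. On that reading, treated HCV is eligible after the interval, untreated HCV is eligible if RNA is undetectable, and untreated current HCV stays out. This is probably what the sponsor meant, and that part of the reply stands. But the bullet nowhere limits *ongoing* to treated infection, and sentence 1 carries no qualifier.

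The comparison with E 03 is also open to challenge. Its bullets admit bounded subsets under stated limits and do not reverse the heading for the very group it names. The nearer neighbour is the first HBV bullet of E 16, which sets conditions that carry out the heading. That weakens the case for enrolling but does not remove the sentence that allows it.

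Two stronger readings are tempting. First, a reader might infer a measured hepatic hazard from the liver enzyme elevations with pembrolizumab reported in Section 4.3. Those data are not broken down by HCV status, and no text at hand links HCV viraemia to added risk with this combination. Nor does hepatic safety rest on E 16. Table 5 lists entry exclusion for impaired liver function, clinical monitoring, regular liver tests and dose-modification guidance, while E 27, E 28 and E 30 cap bilirubin, transaminases and clotting times however E 16 is read. Second, a reader might infer that a site is forced to enroll. It is not: E 33 excludes a "Participant not suitable for participation, whatever the reason, as judged by the Investigator", and E 36 gives similar discretion.

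**Conclusion.** The point holds in a narrow form. E 16 and its German copy give opposite answers for participants with known, untreated HCV and detectable RNA. Context suggests that exclusion is intended, but the text does not say so, and sites could enroll inconsistently.

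This is one defect printed in two places. The documents give no HCV prevalence, so the number of participants affected is unknown. The liver-function limits and investigator discretion give partial protection, but neither makes the HCV rule uniform across sites. No response-rate, sample-size or interim figure changes.

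A reader might also infer that treated participants should have to show undetectable RNA. The protocol sets no such condition, and the conflict does not involve them. Adding one would narrow eligibility beyond the defect. It would also need a test whose timing is not clearly scheduled outside Germany and Italy: footnote f of Table 4 gives no time point for HCV RNA, and footnote h of the Schedule of Activities limits the screening tests elsewhere to known infection under antiviral treatment.

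The conclusion assumes that no text outside the pages at hand resolves the case. A separate HCV rule in substudy 03 could settle it for Cohort C but would not repair the common criterion.

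**What to change.** In E 16 and in the German E 16 of Section 10.7, replace the first two sentences of the HCV bullet with:

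*Participants whose HCV infection is past, or has been treated, are eligible provided that any anti-HCV treatment given ended at least 1 month before study intervention starts. Participants with untreated HCV infection and detectable HCV RNA are excluded.*

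Keep the third sentence as it is. If the sponsor wants untreated viraemic participants in a particular cohort, for example the hepatocellular carcinoma cohort, state the exception for that cohort and narrow the lead sentence to match. E 25 and E 28 already carry exceptions for Cohort C, so there is a model to follow.

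The cost is a change of wording in two places. It adds no condition for treated participants and no test beyond the HCV RNA already required after positive serology.

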5.3 LIFESTYLE CONSIDERATIONS

5.3.1 Meals and dietary restrictions

No food or drink restrictions are required. Guidelines on fluid intake are presented in [Section 6.1.3](#).

5.3.2 Caffeine, alcohol, and tobacco

No restrictions are required.

5.3.3 Activity

Participants are advised to abstain from strenuous exercise and avoid long hot showers and saunas on Days 1 to 4 of every treatment cycle.

5.3.4 Hydration

Since SAR444245 may induce episodes of hypotension, participants should be informed of the importance of being well hydrated and be provided with hydration instructions. Guidelines pertaining to fluid intake on the day of SAR444245 dosing and for the 3 days after administration are detailed in [Section 6.1.3](#).

5.4 SCREEN FAILURES

Screen failures are defined as participants who consent to participate in the clinical study but are not subsequently enrolled. A minimal set of screen failure information is required to ensure transparent reporting of screen failure participants to meet the Consolidated Standards of Reporting Trials (CONSORT) publishing requirements and to respond to queries from regulatory authorities. Minimal information includes demography, screen failure reasons, eligibility criteria, and any serious adverse event (SAE).

Individuals who do not meet the criteria for participation in this study (screen failure) and for whom resolution of the screen failure reason may not be expected within a reasonable time frame, will be recorded as screen failures. In case the participant is a temporary screen failure (ie, prolonged screening), there is no need to have participant re-consent (ie, new ICF signed) if the participant finally participates in the trial. However, if the reason for temporary screen failure is a reason that might have altered the initial given agreement of the participant to participate, the Investigator should ensure the willingness of the participant to continue or redo some screening procedures and his/her participation to the trial. This oral agreement should be documented in the participant's chart. All the tests out of protocol window should be repeated and entered to the additional pages.

Individuals who do not meet the criteria for participation in this study (screen failure) may be rescreened once only. A participant who screen failed may be rescreened; in this situation, the rescreened participant should sign a new ICF. A participant may be rescreened only once. Rescreened participants should be assigned a different participant number as for the initial screening.

5.5 CRITERIA FOR TEMPORARILY DELAYING ENROLLMENT/RANDOMIZATION/ADMINISTRATION OF STUDY INTERVENTION

During a regional or national emergency declared by a governmental agency, if the site is unable to adequately follow protocol-mandated procedures, contingency measures are proposed in [Section 10.9](#).

